
The CTSU Web site is located at https://www.ctsu.org
		

Accrual = 145

Cycle = 28 days

All doses are based on actual body weight.

---

1. Treatment will continue for up to 13 cycles (approximately 1 year).

## 1. Introduction

### 1.1 Rationale for selected approach and trial design

Patients with advanced pancreatic neuroendocrine tumors (NETs) currently have few treatment options that yield objective radiographic tumor regression. Recent studies evaluating everolimus and sunitinib in this patient population have demonstrated prolongation of progression-free survival (PFS) compared to placebo, but overall tumor response rates (by RECIST) with these agents are less than 10%.

Historical studies reporting the highest response rates (RRs) and longest PFS intervals include regimens with cytotoxic chemotherapy. In an initial randomized study of 106 patients, Moertel *et al.* reported activity associated with the combination of streptozocin and doxorubicin in patients with advanced islet-cell tumors. The RR associated with this regimen was reported to be 69% and PFS was 20 months. However, because of the use of non-standard response criteria, the true objective radiologic response rate was likely much lower. Retrospective series have reported overall response rates of 6-39% and PFS of 4-18 months associated with streptozocin-based regimens in pancreatic NETs. While clearly associated with activity, the combination of streptozocin and doxorubicin is also associated with considerable toxicity, including myelosuppression, asthenia, and renal insufficiency, precluding its routine use in this disease.

Recent retrospective series and small, prospective phase II studies, described below, suggest that temozolomide is similarly active but less toxic than streptozocin-based therapy in patients with pancreatic NETs. Furthermore, like streptozocin, temozolomide is an alkylating agent that induces methylation at the O6 position of guanine, suggesting that expression of the DNA repair enzyme methyl guanine methyltransferase (MGMT) may correlate with treatment response to temozolomide. Based on these studies, temozolomide-based therapy is listed on NCCN guidelines and is included in the Medicare compendium for use in pancreatic NETs. There is, nevertheless, little consensus on the optimal temozolomide regimen to use in patients with pancreatic NETs, nor has temozolomide been evaluated prospectively in a multi-institutional setting in patients with advanced pancreatic neuroendocrine tumors.

The proposed study will provide prospective data on response rates and progression-free survival associated with temozolomide or temozolomide in combination with capecitabine, and will also assess the relative efficacy of these two regimens. The study further explores whether, as has been shown in glioblastoma, MGMT deficiency as determined by promoter methylation and immunohistochemistry, predicts response in patients with pancreatic NETs treated with these regimens.

We propose a multi-institutional randomized study of temozolomide administered with or without capecitabine in advanced pancreatic neuroendocrine tumor patients (using dosing as per the Strosberg regimen). The principal objective of the study will be to evaluate PFS associated with temozolomide alone or temozolomide and capecitabine in patients with advanced pancreatic neuroendocrine tumors. Secondary objectives will be to assess the tumor response rates, overall survival, and toxicity associated with these regimens. A

correlative study will assess whether MGMT deficiency is associated with temozolomide response.

1.2 Clinical relevance of study

Streptozocin-based therapy was associated with a survival benefit in one randomized study of pancreatic NETs and is currently the only FDA-approved cytotoxic agent for use in this disease. However, because of its potential for toxicity and production shortage, its use in pancreatic NETs is not widespread. Both retrospective and small, prospective studies suggest that temozolomide-based regimens are an active and potentially less toxic oral alternative to streptozocin-based therapy in pancreatic NETs. Based on these studies, temozolomide is increasingly used for this indication and is included in both NCCN guidelines and the Medicare compendium.

There have been no prospective studies evaluating the antitumor activity of temozolomide alone in patients with neuroendocrine tumors. Similarly, the current common use of a temozolomide/capecitabine combination regimen is based on data from a 30-patient, retrospective, single-institution series; the temozolomide/capecitabine regimen has not been formally evaluated in a prospective phase II study. A need to formally evaluate the activity of temozolomide in pancreatic neuroendocrine tumors, and to compare single agent vs. combination therapy in this disease was highlighted in the NCI Neuroendocrine Tumor Clinical Trials Planning Meeting (CTPM).

The currently proposed study responds to this recommendation. We note that temozolomide alone is considered the reference arm for this study, despite the absence of prospective data for this combination in neuroendocrine tumors. We considered several alternative options in making this decision. Ideally, a placebo arm would be used as a reference, as was done in the RADIANT 3 and sunitinib randomized studies. However, a placebo was not considered appropriate or feasible in light of the fact that temozolomide is included in treatment compendia based on retrospective and small prospective series demonstrating antitumor activity. A streptozocin control arm was not considered feasible based on toxicity concerns, as well as, concerns regarding drug supply. A control arm of everolimus or sunitinib was considered; however, there was little enthusiasm for directly comparing a cytotoxic chemotherapy regimen to a targeted agent. Indeed, a current treatment paradigm is starting with targeted therapy in most patients, and using a cytotoxic regimen as a salvage therapy. A goal of this study is to establish clear prospective data for two promising cytotoxic regimes and to gain a preliminary assessment of their relative activity.

Additionally, preliminary data described in the correlative section of this proposal suggest that the anti-tumor activity of temozolomide is associated with the DNA repair enzyme MGMT. The identification of biomarkers predictive of tumor response was an additional recommendation of the Neuroendocrine Tumor CTPM. Data derived from studies in glioblastoma strongly suggest a correlation between MGMT silencing and response to temozolomide-based therapy, as does retrospective data in pancreatic neuroendocrine tumors. The correlative component of this study will assess whether MGMT promoter methylation status is associated with the activity of temozolomide-based therapy. A positive association could provide justification for the use of MGMT expression as a

determinant for which pancreatic neuroendocrine tumor patients should receive temozolomide-based treatment.

1.3 All relevant data that justify the use of the control and experimental arms

Antitumor activity associated with temozolomide in neuroendocrine tumors has been reported in a number of retrospective series. In a retrospective series of 36 patients treated with temozolomide monotherapy, tumor regression was observed in 31% of bronchial carcinoid tumors and 8% of pancreatic neuroendocrine tumors; median time to progression (TTP) was 7 months for all patients. In a series of 97 patients, 18 of 53 patients with pancreatic NETs (34%) achieved a partial or complete response to temozolomide-based therapies; median PFS was 13.6 months for those patients. A third retrospective series of 21 patients treated with temozolomide monotherapy demonstrated responses in 25% of pancreatic NETs, median PFS was 9.1 months.

Temozolomide has additionally been investigated prospectively in small phase II studies of patients with neuroendocrine tumors, though always in combination with other agents. In an initial study, 29 patients with metastatic neuroendocrine tumors were treated with a combination of temozolomide, administered at a dose of 150 mg/m^2 for 7 days, every other week, and thalidomide at doses of 50 to 400 mg daily; this combination was associated with objective tumor responses in 5/11 patients. Median PFS was not reached. A subsequent phase II study evaluated the combination of temozolomide and bevacizumab in 34 patients with neuroendocrine tumors (15 pancreatic, 19 carcinoid). Patients received temozolomide, 150 mg/m^2/day po for 7 days every other week, and bevacizumab, 5 mg/kg IV every other week. Due to anticipated lymphopenia, patients also received prophylaxis with trimethoprim/sulfamethoxazole (1 DS tablet q MWF). Objective tumor responses were observed in 33% of patients with pancreatic neuroendocrine tumors with median PFS of 14.3 months for these patients ([name], personal communication). In a third prospective study a regimen of temozolomide and everolimus was associated with an overall tumor response rate of 35% in patients with advanced pancreatic NET, median PFS was not reported.

Interestingly, pre-clinical and early clinical evidence suggest that capecitabine may be synergistic with temozolomide. In a series of 17 patients with pancreatic NETs, combination therapy with temozolomide and capecitabine was associated with a tumor response rate of 59%, median PFS was not reported. A recent single-institution retrospective study by Strosberg *et al.* reported response rates of 70% and a median PFS of 18 months in 30 patients with advanced pancreatic NETs. In this study, temozolomide was administered at a dose of 200 mg/m^2 days 10-14, and capecitabine was administered at a dose of 750 mg/m^2 BID d1-14. The combination and specific dosing schedules reported were very well tolerated with only 4 patients experiencing grade 3 or 4 adverse events (anemia, thrombocytopenia, elevated AST and elevated ALT). The most common grade 1 and 2 adverse events were fatigue, nausea, myelosuppression and hand-foot syndrome. Based on this study, the combination of temozolomide and capecitabine has become popular and commonly used in patients with advanced pancreatic neuroendocrine tumors.

Taken together, these prospective and retrospective studies suggest that temozolomide-based therapy is comparable to streptozocin-based regimens and might reasonably be expected to be associated with an overall median PFS of 7-14 months in patients with advanced pancreatic NET. To date, no prospective studies have evaluated the antitumor activity of temozolomide alone in pancreatic neuroendocrine tumors, nor have any prospective studies formally evaluated the combination of temozolomide and capecitabine in this setting. As noted above, despite the absence of prospective data, temozolomide alone is considered a reference arm in this study based on the strength of prior retrospective and limited prospective data demonstrating activity with temozolomide containing regimens in this setting, and the inclusion of temozolomide in treatment compendia. Strong historical control data from the placebo arms of the randomized studies of everolimus (showing a PFS of 5.5 months) and sunitinib (showing a PFS of 4.5 months) should provide a reasonable basis for assessment of the antitumor activity associated with temozolomide alone. Additionally, these two regimens have never been formally compared.

The proposed study will compare the temozolomide/capecitabine combination (as reported by Strosberg and colleagues), in which temozolomide is administered during a 28 day cycle at a dose of 200 mg/m^2 days 10-14 of 28 day cycles and capecitabine is administered at a dose of 750 mg/m^2 BID days 1-14 of 28 day cycles, to single agent temozolomide. We note that prior prospective studies of temozolomide have used a dose-intense regimen of 150 mg/m^2 for 7 days, administered every other week, but that this regimen has been associated with significant lymphopenia and need for prophylaxis. To reduce this risk, and to facilitate comparison with the combination regimen, we have elected to use a single-agent temozolomide regimen of 200 mg/m^2 days 1-5 of a 28-day regimen in our study. We further plan to limit the total duration of treatment to 13 cycles (approximately 1 year).

#### 1.4 Rationale for Laboratory Research Studies

##### 1.4.1 Evaluation of MGMT status by Immunohistochemistry (IHC)

Temozolomide is an alkylating agent initially developed as an oral and more easily tolerated alternative to dacarbazine. The cytotoxic effect of temozolomide has been attributed to its ability to induce DNA methylation at the O6 position of guanine. Methylation of guanine results in DNA mismatch, ultimately resulting in apoptosis and tumor cell death. The sensitivity of tumor cells to alkylating agents, including temozolomide, has been associated with decreased levels of the DNA repair enzyme, O6-methylguanine DNA methyltransferase (MGMT), which, through its ability to restore DNA to its normal form, can prevent chemotherapy-induced cell death. Decreased levels of MGMT have been associated with clinical benefit and enhanced survival in melanoma and glioblastoma patients treated with temozolomide.

In a study by Kulke, et al., 97 archival neuroendocrine tumors specimens were evaluated for MGMT deficiency by immunohistochemistry. Among 37 pancreatic neuroendocrine tumors evaluated, 19 (51%) were MGMT deficient. Non-functional tumors included similar proportions of MGMT intact and MGMT deficient

tumors. Three of 10 insulinomas were MGMT deficient; both gastrinomas and the single evaluated glucagonoma were also MGMT deficient. In contrast, MGMT was present in all 60 carcinoid tumors (20 typical bronchial carcinoids, 20 atypical bronchial carcinoids and 20 small intestine carcinoids) evaluated. Among 21 patients with evaluable tumor tissue who had also received treatment with temozolomide, 4 of 5 patients with MGMT-deficient tumors (all pancreatic NETs) and 0 of 16 patients with MGMT-intact tumors responded to treatment ( $p=0.001$ ).

#### 1.4.2 Evaluation of MGMT status by Promoter Methylation

The clinical utility of assessing MGMT promoter methylation status was first demonstrated in patients with gliomas. Gliomas are the most common primary brain tumors. Grade IV gliomas, also known as glioblastoma multiforme (GBM) are highly malignant tumors that account for almost a third of primary brain tumors in adults. Patients with gliomas that exhibited promoter methylation of the MGMT gene showed modestly longer survival after treatment with alkylating chemotherapeutics than patients whose gliomas did not show MGMT promoter methylation. Clinical trials to evaluate the use of MGMT promoter methylation to predict response to alkylating agents have also been designed for patients with acute myeloid leukemia, neuroendocrine tumors, and other cancers.

The mechanisms of MGMT regulation in neuroendocrine tumors remain unknown. Silencing of the MGMT gene by CpG island promoter methylation is a common mechanism of MGMT regulation in other tumor types. In patients with glioblastoma, MGMT promoter methylation is associated with improved survival and benefit from temozolomide. Limited studies of CpG island methylation in neuroendocrine tumors however, have found either no significant difference in MGMT promoter methylation rates between carcinoid and pancreatic neuroendocrine tumors, or higher rates of promoter methylation in carcinoid tumors compared to pancreatic neuroendocrine tumors.

Further studies to evaluate whether promoter methylation is a common MGMT silencing mechanism in neuroendocrine tumors, and whether promoter methylation correlates with immunohistochemical absence of MGMT, are warranted.

## 2. Objectives

### 2.1 Primary Endpoints

2.1.1 To evaluate PFS associated with temozolomide alone or temozolomide and capecitabine in patients with advanced pancreatic neuroendocrine tumors.

### 2.2 Secondary Endpoints

2.2.1 To evaluate response rates (RR) associated with temozolomide alone or temozolomide and capecitabine treatment in patients with advanced pancreatic neuroendocrine tumors.

2.2.2 To evaluate overall survival (OS) associated with temozolomide alone or temozolomide and capecitabine in patients with advanced pancreatic neuroendocrine tumors.

2.2.3 To evaluate the toxicity associated with temozolomide alone or temozolomide and capecitabine treatment in patients with advanced pancreatic neuroendocrine tumors.

2.2.4 To evaluate the usefulness of MGMT status (by IHC and promoter methylation) for predicting response in pancreatic neuroendocrine tumor patients treated with either temozolomide or temozolomide and capecitabine.

2.2.5 To bank radiology images for evaluation of quality, reproducibility, and compliance with CT methodology.

Rev. 7/15

### 3. Selection of Patients

Each of the criteria in the checklist that follows must be met in order for a patient to be considered eligible for this study. Use the checklist to confirm a patient's eligibility. For each patient, this checklist must be photocopied, completed and maintained in the patient's chart.

**In calculating days of tests and measurements, the day a test or measurement is done is considered Day 0. Therefore, if a test is done on a Monday, the Monday four weeks later would be considered Day 28.**

**ECOG-ACRIN Patient No.** \_\_\_\_\_

**Patient's Initials (L, F)** \_\_\_\_\_

**NOTE:** All questions regarding eligibility should be directed to the study chair or study chair liaison.

**NOTE:** Institutions may use the eligibility checklist as source documentation if it has been reviewed, signed, and dated prior to randomization by the treating physician.

#### 3.1 Eligibility Criteria

- \_\_\_\_\_ 3.1.1 Patient must have histologically or pathologically confirmed locally unresectable or metastatic low or intermediate grade pancreatic neuroendocrine tumor, excluding small cell carcinoma.
- \_\_\_\_\_ 3.1.2 Patient must have measurable disease by RECIST 1.1 criteria as defined in Section [6.1.2](#). Baseline measurements and evaluations of all sites of disease must be obtained  $\leq$  4 weeks prior to randomization and must be acquired by multiphasic CT or contrast MRI.
- \_\_\_\_\_ 3.1.3 Patient must have documented disease progression, and date of last documented disease progression must be within 12 months from date of randomization.
- \_\_\_\_\_ 3.1.4 Patient must not have received prior temozolomide, DTIC, capecitabine, or 5-FU therapy.
- \_\_\_\_\_ 3.1.5 Prior everolimus and/or sunitinib therapy is allowed, so long as it was discontinued  $\geq$  4 weeks prior to randomization.
- \_\_\_\_\_ 3.1.6 Concurrent somatostatin analogues are allowed provided that the patient 1) has been on a stable dose (+/- 10mg) for 8 weeks and 2) has documented disease progression on that dose.
- \_\_\_\_\_ 3.1.7 Chemoembolization is allowed if  $\geq$  4 weeks from study entry. There are 3 possible scenarios:
  - \_\_\_\_\_ 3.1.7.1 If patient has hepatic disease only: they need to have progressed in the liver since chemoembolization and have measurable disease by RECIST 1.1 in order to be eligible.
  - \_\_\_\_\_ 3.1.7.2 If patient has hepatic and extrahepatic disease: they will need to have progressed inside OR outside the liver and

have measurable disease by RECIST 1.1 in order to be eligible.

- 3.1.8 Patients may not be receiving any other investigational agents while on study treatment.
- 3.1.9 Patients may not be receiving Coumadin while on treatment. Other anticoagulants are allowed.
- 3.1.10 Patients must have normal organ and marrow function as defined below within  $\leq$  14 days prior to randomization:
  - 3.1.10.1 Leukocytes  $\geq$  3,000/mm^3  
Leukocytes \_\_\_\_\_ Date: \_\_\_\_\_
  - 3.1.10.2 Absolute neutrophil count  $\geq$  1,500/mm^3  
Neutrophil count: \_\_\_\_\_ Date: \_\_\_\_\_
  - 3.1.10.3 Hemoglobin  $\geq$  9 g/dL  
Hemoglobin: \_\_\_\_\_ Date: \_\_\_\_\_
  - 3.1.10.4 Platelets  $\geq$  100,000/mm^3  
Platelets: \_\_\_\_\_ Date: \_\_\_\_\_
  - 3.1.10.5 Total bilirubin  $\leq$  institutional upper limit of normal (ULN) or  $\leq$  1.5 X institutional ULN (if the patient has liver metastases).  
ULN: \_\_\_\_\_ Bilirubin: \_\_\_\_\_ Date: \_\_\_\_\_
  - 3.1.10.6 AST(SGOT)/ALT(SGPT)  $\leq$  3 X institutional ULN or ( $\leq$  5 X institutional ULN if the patient has liver metastases).  
ULN: \_\_\_\_\_ AST \_\_\_\_\_ Date: \_\_\_\_\_  
ULN: \_\_\_\_\_ ALT \_\_\_\_\_ Date: \_\_\_\_\_
  - 3.1.10.7 Serum Creatinine  $\leq$  1.5 X institutional ULN  
ULN: \_\_\_\_\_ Creatinine: \_\_\_\_\_ Date: \_\_\_\_\_
- 3.1.11 Patient must be at least 18 years of age.
- 3.1.12 Patient must have ECOG performance status 0-1.
- 3.1.13 Patient must have life expectancy  $\geq$  12 weeks.
- 3.1.14 Patients with either clinically apparent central nervous system metastases or carcinomatous meningitis are ineligible.
- 3.1.15 Patients must NOT have active or uncontrolled infection or serious medical or psychiatric illness.
- 3.1.16 Patients must NOT have history of allergic reactions attributed to compounds of similar chemical or biologic composition to temozolomide or capecitabine.

\_\_\_\_\_ 3.1.17 Patient must NOT have absorption issues that would limit the ability to absorb study agents.

\_\_\_\_\_ 3.1.18 Patients with a history of the following within  $\leq$  12 months of study entry are not eligible.

- Arterial thromboembolic events: Yes \_\_\_\_\_ Date: \_\_\_\_\_ No: \_\_\_\_\_
- Unstable angina: Yes \_\_\_\_\_ Date: \_\_\_\_\_ No: \_\_\_\_\_
- Myocardial Infarction: Yes \_\_\_\_\_ Date: \_\_\_\_\_ No: \_\_\_\_\_

\_\_\_\_\_ 3.1.19 Patients with symptomatic peripheral vascular disease are not eligible.

\_\_\_\_\_ 3.1.20 Patients must NOT have previous or concurrent malignancy. Exceptions are made for patients who meet any of the following conditions:

- Non-melanoma skin cancer, in situ cervical cancer, or breast cancer in situ.

OR

- Prior malignancy completely excised or removed and patient has been continuously disease free for  $>$  5 years.

OR

- Prior malignancy cured by non-surgical modalities and patient has been continuously disease free for  $>$  5 years.

Date of last evidence disease: \_\_\_\_\_

\_\_\_\_\_ 3.1.21 Women must not be pregnant or breast-feeding due to potential harm to fetus from temozolomide and/or capecitabine.

All females of childbearing potential must have a blood test or urine study within  $\leq$  2 weeks prior to randomization to rule out pregnancy. A female of childbearing potential is any woman, regardless of sexual orientation or whether they have undergone tubal ligation, who meets the following criteria: 1) has not undergone a hysterectomy or bilateral oophorectomy; or 2) has not been naturally postmenopausal for at least 24 consecutive months (i.e., has had menses at any time in the preceding 24 consecutive months).

Female of childbearing potential? \_\_\_\_\_ (Yes or No)

Date of blood test or urine study: \_\_\_\_\_

\_\_\_\_\_ 3.1.22 Women of childbearing potential and sexually active males must be strongly advised to use an accepted and effective method of contraception or to abstain from sexual intercourse for the duration of their participation in the study. Should a woman become pregnant while participating in this study, she should inform her treating physician immediately. If a man impregnates a woman while participating in this study, he should inform his treating physician immediately.

---

- 3.1.23 Patient must be able to swallow pills.
- 3.1.24 Patient must be able to tolerate CT or MR imaging including contrast agents as required for their treatment and the protocol.

---

Physician Signature

---

Date

**OPTIONAL:** This signature line is provided for use by institutions wishing to use the eligibility checklist as source documentation.

Rev. 6/14

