## 6. Measurement of Effect

### 6.1 Antitumor Effect – Solid Tumors

For the purposes of this study, patients should be re-evaluated for response every 12 weeks. In addition to a baseline scan, confirmatory scans should also be obtained 4 weeks following initial documentation of objective response.

Response and progression will be evaluated in this study using the international criteria proposed by the revised Response Evaluation Criteria in Solid Tumors (RECIST) guideline (version 1.1) [Eur J Ca 45:228-247, 2009]. Changes in the largest diameter (unidimensional measurement) of the tumor lesions and the shortest diameter in the case of malignant lymph nodes are used in RECIST.

The following general principles must be followed:

1. To assess objective response, it is necessary to estimate the overall tumor burden at baseline to which subsequent measurements will be compared. All baseline evaluations should be performed as closely as possible to the beginning of treatment and **never more than four weeks** before randomization.
2. Measurable disease is defined by the presence of at least one measurable lesion.
3. All measurements should be recorded in metric notation by use of a ruler or calipers.
4. The same method of assessment and the same technique must be used to characterize each identified lesion at baseline and during follow-up.

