#### 6.1.2 Disease Parameters

##### Measurable Disease

Measurable lesions are defined as those that can be accurately measured in at least one dimension (longest diameter to be recorded) as  $\geq 20$  mm by chest x-ray, as  $\geq 10$  mm with CT scan, or  $\geq 10$  mm

with calipers by clinical exam. All tumor measurements must be recorded in millimeters.

**NOTE:** Tumor lesions that are situated in a previously irradiated area are measurable if they demonstrate recent evidence of progression.

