#### Target Lesions

All measurable lesions up to a maximum of 2 lesions per organ and 5 lesions in total, representative of all involved organs, should be identified as **target lesions** and recorded and measured at baseline. Target lesions should be selected on the basis of their size (lesions with the longest diameter), be representative of all involved organs, but in addition should be those that lend themselves to reproducible repeated measurements. It may be the case that, on occasion, the largest lesion does not lend itself to reproducible measurement in which circumstance the next largest lesion which can be measured reproducibly should be selected.

A sum of the diameters (longest for non-nodal lesions, short axis for nodal lesions) for all target lesions will be calculated and reported as the baseline sum diameters. If lymph nodes are to be included in the sum, then only the short axis is added into the sum. The baseline sum of the diameters will be used as reference to further characterize any

objective tumor regression in the measurable dimension of the disease.

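### Chemoembolized liver lesions that have not progressed since the procedure can be target lesions, so shrinkage from embolization can be counted as drug response

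*Combined protocol and SAP*

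**What the plan says.** Section 3.1 allows prior chemoembolization if it took place at least 4 weeks before study entry.

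- **Liver-only disease (3.1.7.1):** "they need to have progressed in the liver since chemoembolization".
- **Liver plus extrahepatic disease (3.1.7.2):** "they will need to have progressed inside OR outside the liver". There is no reference to the procedure.
- **All patients (3.1.3):** "date of last documented disease progression must be within 12 months from date of randomization". This is tied neither to a site nor to chemoembolization.

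Sections 3.1.2 and 6.1 allow the baseline scan up to 4 weeks before randomization.

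In section 6.1.2, "Target lesions should be selected on the basis of their size (lesions with the longest diameter), be representative of all involved organs". The limits are two per organ and five in total, and the lesions must be reproducibly measurable. For one kind of local treatment there is a safeguard: "Tumor lesions that are situated in a previously irradiated area are measurable if they demonstrate recent evidence of progression". Nothing comparable is written for embolized lesions.

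Section 6.1.4.1 defines partial response as a fall of at least 30% in the target sum from baseline, and progression as a rise of at least 20% (and 5 mm) from the smallest sum on study. Prior chemoembolization is not among the stratification factors in sections 4.5 and 9.2.

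**The concern.** Two neighbouring criteria deal with the same prior procedure but set different conditions, and the looser one leads into the endpoint. Under 3.1.7.2 a patient whose nodes have grown can enter while the embolized liver lesions are stable or still shrinking. If those lesions are targets, further shrinkage after baseline lowers the sum just as a drug effect would, and no rule separates the two causes.

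At stake is mainly objective 2.2.1, the response rate with each regimen. Randomization protects the comparison of arms on average, but it does not protect the estimate within an arm. A response credited to embolization can only convert a non-responder, so it adds more to the arm with the lower rate and narrows the difference. At about 69 patients per arm, chance imbalance in prior chemoembolization is also possible.

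**Working it through.** **1. Does the text admit such a patient?** Take a patient with liver and nodal disease, chemoembolized more than 4 weeks before entry, whose nodes have since progressed while the treated liver lesions have not. The patient meets 3.1.3 (progression within 12 months), the 4-week gap, and 3.1.7.2 (progression outside the liver). Reading the words of 3.1.7.1 about timing into 3.1.7.2 changes nothing here, because the nodal progression already follows the procedure.

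**2. Can the treated lesions be targets?** Yes. Section 6.1.2 selects by size, organ and reproducibility. Its only condition on prior local treatment concerns irradiation.

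**3. Can shrinkage from embolization fall after baseline?** Yes. Taking study entry as randomization, a procedure just over 4 weeks before entry and a scan at the far end of the 4-week window put baseline within days of the procedure. That is the extreme case, since section 6.1 also wants baseline as near the start of treatment as possible.

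**4. The plan's own response-rate figure.** Section 9.3 gives 138 patients (138/2 = 69 per arm), 33% v 53%, Fisher's exact test at two-sided 20%, and at least 80% power. Exact enumeration gives 82.4%, so the plan's figure is confirmed.

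**5. Sensitivity of the response rate.** The documents supply neither input, so both are assumptions:
- f = share of each arm entering with unprogressed embolized target lesions, 5-15%
- q = chance that a would-be non-responder among them reaches partial response through embolization, 25-50%

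Observed rate = RR + f × q × (1 − RR).

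| f | q | Temozolomide | Combination | Difference (points) | Fisher power |
|---|---|---|---|---|---|
| 0 | – | 33% | 53% | 20 | 82.4% |
| 5% | 25% | 33.8% | 53.6% | 19.75 | 81.6% |
| 10% | 50% | 36.3% | 55.3% | 19.0 | 78.9% |
| 15% | 50% | 38.0% | 56.5% | 18.5 | 77.1% |

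Last row: 0.33 + 0.15 × 0.50 × 0.67 = 0.380 and 0.53 + 0.15 × 0.50 × 0.47 = 0.565. The difference is 0.20 × (1 − f × q) = 0.20 × 0.925 = 0.185. One extra response adds 1/69 = 1.4 points to an arm.

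**6. PFS.** Section 9.3 states at least 81% power for medians of 9 v 14 months with 105 events, two-sided 0.20, and an O'Brien-Fleming interim at 80 events. With the interim included, power is 82.7-83.3% (Schoenfeld) or 81.8-82.3% (Freedman), the range reflecting a hazard ratio of 9/14 or 0.64. The plan's figure is again confirmed.

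Now suppose, only to test the consequence, that progression is delayed by 3 to 6 months in 10-20% of both arms, or by 6 months in 30%. The medians become 9.3-11.1 and 14.3-16.0 months. In simulation without the interim look, the hazard ratio stays at about 0.63-0.64, power at about 83-84% (83.7% with no delay), and type I error at about 0.20.

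**The case against.** The strongest reply is that each step is possible rather than certain. Targets must be reproducibly measurable, only two are taken per organ, and untreated liver lesions may be chosen instead. Only shrinkage after a post-procedure baseline counts, and the documents contain no data on it. If the growing nodes are measurable, they belong in the same sum, so the liver lesions must shrink by more than 30% to yield a partial response. All of this stands. It limits the size of the effect but does not close the route.

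A second reply is that 3.1.7.2 sits directly beneath 3.1.7.1 and can be read as carrying the same reference to the procedure, while the capitalized OR looks like a deliberate choice to accept extrahepatic progression. The first half is a fair reading of an ambiguous text. The second half supports the point: if entry on extrahepatic progression is intended, the protection has to come from the target-lesion rule, and that rule is missing.

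A reader might infer that embolization prolongs PFS. The documents do not support that. Shrinkage can offset growth elsewhere in the sum, but it also lowers the nadir from which progression is judged, and under sections 6.1.4.2 and 6.1.4.3 new lesions and unequivocal non-target progression still end PFS. Even if a delay is assumed, it acts on both arms and leaves the log-rank comparison essentially where it was. The reading of temozolomide against historical placebo PFS in section 1.3 is informal, with no test or threshold attached.

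The announcement "There are 3 possible scenarios" is followed by two items in the text available here. The third may have been lost in conversion of the document, or the two halves of 3.1.7.2 may have been counted separately. Nothing here rests on it.

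**Conclusion.** The gap in 3.1.7.2 and the missing rule for embolized lesions in 6.1.2 are both in the text. Together they allow shrinkage from embolization to be recorded as drug response. The consequence is modest and falls mainly on the response rate. Over the assumed ranges the temozolomide rate rises by 0.8 to 5.0 points and the combination rate by 0.6 to 3.5 points. For scale, section 9.3 expects a 90% confidence interval up to 21 points wide within each arm. The difference narrows from 20 to between 19.75 and 18.5 points, and power falls from 82.4% to between 81.6% and 77.1%, the lower part being below the stated 80%.

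It is tempting to say that a 5-point rise is a quarter of the 20-point target difference. That sets one arm's inflation against a between-arm contrast. Both arms rise together, so the difference loses at most 1.5 points within these ranges. A loss of a quarter would need the affected patients to fall in one arm only.

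These sizes rest entirely on the assumed f and q. The primary log-rank comparison is not systematically biased, although chance imbalance remains possible.

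**What to change.** 1. In section 6.1.2, extend the irradiated-lesion rule: a chemoembolized lesion may be a target only if it has progressed since the procedure, and is otherwise recorded as non-target. Unequivocal progression of a non-target lesion still counts, so it remains under observation. This is the change that matters most.
2. Reconcile 3.1.7.2 with 3.1.7.1 by stating whether the qualifying progression must postdate chemoembolization. Adding that condition alone would not be enough, because patients who progressed only outside the liver would still enter with unprogressed embolized lesions.
3. For patients already enrolled, prespecify a sensitivity analysis of response rate and PFS that excludes those with unprogressed embolized target lesions. Status must be judged from baseline information, so the procedure date and the state of each treated lesion need to be recorded.
4. Check the count of scenarios in 3.1.7 against the source document.

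The cost is a short amendment to the eligibility checklist and section 6.1.2. A few patients with no other measurable lesion would have to wait until they progress, a small loss of accrual in a disease that section 9.1 describes as relatively rare. Showing progression since the procedure also requires a suitable comparison scan, which some patients may not have.
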